## **6.6 Precautions/Overdosage**

Precautions and overdosage are described in the labelling of the product.

The patients are already under treatment with levothyroxine and with PPIs at stable doses, therefore an evaluation of the precautions for use has already been done at the time of prescription and during the periodic monitoring of the diseases.

Since the patients are routinely under treatment with levothyroxine and PPIs, the risk of overdosage should be minimal.

## **6.7 Treatment allocation and randomisation procedures**

The study is a non-randomized study.

## 6.8 Emergency code and unblinding procedures

This is an open study; therefore unblinding procedures are not needed.

## 7 STUDY PROCEDURES

### 7.1 Overall study schedule

Study schedule is summarized at page 11.

### 7.2 Screening/Inclusion

#### *Visit 1 - Day -28/-42 (Screening Visit)*

The screening procedures (Visit 1) will be performed between 4 and 6 weeks prior to inclusion.

Patients will be screened by endocrinologists.

Subjects should come to the clinical center holding their morning dose of LT4 and possibly bringing with them the box of the LT4 and PPI that they are on therapy with for a visual check by the Investigator. They will be asked to sign the Informed Consent Forms before the start of any screening procedures.

The screening visit will include:

- informed consent;
- demography;
- medical and medication history;
- general physical examination (including neck exam, cardiac exam, and respiratory exam);
- body weight (BW), height;
- vital signs (blood pressure [BP], heart rate [HR]);
- check of inclusion/exclusion criteria;
- blood sampling for thyroid function tests (TSH, FT4, FT3, TT3);

---

 The date of the informed consent signature may also precede the date of the screening visit.

- urine pregnancy test (in female subjects of childbearing potential);
- diary dispensing;
- instruction of the patient on how to complete the diary and how to comply with the study requirements (i.e. drugs intake, study restrictions, etc.).

The screened subjects will receive consecutively a Subject N. starting from 001 and preceded by a two-digit code identifying the center (where 01 = [REDACTED]). Should additional centers be involved, these will be identified as 02, 03, 04, etc.) (i.e. 01-001, 01-002, etc. and 02-001, 02-002, etc.), that they will retain from the first Screening Visit until the Final Visit.

Clinical signs/symptoms of hypothyroidism or hyperthyroidism (e.g. palpitations) reported by the patient at the screening visit, if clinically significant, will have to be recorded as medical history in the CRF.

The current LT4 product and dose, as well as the current PPI product and dose will be accurately recorded in the CRF, possibly checking with the medication box/bottle if the patient has brought them with him/her.

Subjects complying with inclusion/exclusion criteria will enter a run-in period, during which they will remain on their current dose of LT4 tablets and will keep taking their PPI as prescribed. Patients will have to fill in a diary reporting the daily intake of LT4 and PPI.

The date of Visit 2 will be scheduled and patients will be asked to come to the clinical center for the next visit, fasting and holding their morning dose of LT4, and bringing with them their diary and possibly the box/bottle of the LT4 and PPI that they are on therapy with.

#### *Re-screenings*

Should the patient require LT4 dose adjustment, it will be possible to re-screen the patient until TSH normalization under the new dose. During re-screenings (not more than 2 re-screenings are allowed) the Investigators should check thyroid function tests (i.e. TSH, FT4, FT3, TT3) at appropriate time intervals (as per [IBSA Pharma Inc 2018](#), 6-8 weeks after dose is changed), as well as the safety of the subjects (adverse events and concomitant medications). Diary will be collected and checked to verify compliance with LT4 and PPI and new diary/ies will be provided to cover the overall screening period. When re-screenings are necessary, the time frame between first screening and baseline visit will be extended, provided that the time interval between re-screening and V2 is kept within -28/-42 days, and that the overall screening period does not exceed 4 months.

### 7.3 Treatment phase

#### *Visit 2 - Day 1 (Baseline and Inclusion Visit)*

Four to six weeks later, the patients will report to the clinical center in the morning at around 8h00 ± 2h, fasting for at least 10 hours and holding their daily dose of levothyroxine and bringing with them their diary and possibly the box/bottle of the LT4 and PPI for:

- adverse events (AEs) and concomitant medications;
- body weight (BW);
- diary collection and check to verify compliance with LT4 and PPI;
- re-check of inclusion/exclusion criteria;
- urine pregnancy test (in female subjects of child bearing potential);
- blood sampling for thyroid function tests (TSH, FT4, TT4, FT3, TT3);
- serum laboratory tests: creatine phosphokinase (CPK), sex-hormone binding globulin (SHBG), ferritin, angiotensin-converting enzyme (ACE), and lipid panel (total cholesterol [TC], high-density lipoprotein cholesterol [HDL-C], low-density lipoprotein cholesterol [LDL-C], very low-density lipoprotein cholesterol [VLDL-C], triglycerides [TG]).
- Tirosint® dispensing;
- diary dispensing;
- remind the patient how to complete the diary and how to comply with the study requirements (i.e. drugs intake, study restrictions, etc.);
- fill in and send the Declaration of Inclusion.

The new onset or the worsening of clinical signs/symptoms of hypothyroidism or hyperthyroidism (e.g. palpitations) reported by the patient, if clinically significant, will have to be recorded as adverse events.

Any changes in the concomitant medications, including the PPI product and/or dose will be recorded in the CRF.

If the subject brings them, the LT4 and PPI box/bottle will be checked to verify changes from the previous visit.

Subjects who are still judged eligible will be dispensed sufficient amount of Tirosint® capsules for treatment up to Visit 3.

The date of Visit 3 will be scheduled and subjects will be asked to come to the clinical center for the next visit, holding their morning dose of LT4, and bringing with them their diary, the box of the PPI that they are on therapy with and the unused, used and partially used boxes and blisters of Tirosint®.

As far as possible, the subjects should begin taking Tirosint the same day of V2, after blood sampling has been performed. The day of first intake of Tirosint will be considered as Day 1 of the study.

***Visit 3 - Day 42±7 (Interim visit)***

Halfway through the treatment period (i.e. 35-49 days after V2), the patients will report to the clinical center in the morning, holding their daily dose of levothyroxine and bringing with them their diary as well as the unused, used and partially used boxes of Tirosint, and the box/bottle of the PPI, and will undergo:

- adverse events (AEs) and concomitant medications;
- blood sampling for thyroid function tests (TSH, FT4, FT3, TT3) for safety check;
- Tirosint® capsules return and count to check compliance;
- diary collection and check to verify compliance with LT4 and PPI;
- Tirosint® dispensing;
- diary dispensing;
- remind the patient how to complete the diary and how to comply with the study requirements (i.e. drugs intake, study restrictions, etc.).

The new onset or the worsening of clinical signs/symptoms of hypothyroidism or hyperthyroidism (e.g. palpitations) reported by the patient, if clinically significant, will have to be recorded as adverse events.

Any changes in the concomitant medications, including the PPI product and/or dose will be recorded in the CRF.

If the subject brings it, the PPI box/bottle will be checked to verify changes from the previous visit.

All the used boxes of Tirosint® will be collected by the Investigator, pills will be counted for check of compliance and drug accountability, and the boxes will be stored by the Investigator or Pharmacist separately from unused supplies. Leftover pills cannot be re-dispensed.

Patients will be dispensed sufficient amount of Tirosint® capsules for treatment up to Visit 4.

The patients will be asked to take their morning LT4 dose only after blood sampling and will continue taking the study medications at the prescribed dose.

The date of Visit 4 will be scheduled and patients will be asked to come to the clinical center for the next visit, fasting and holding their morning dose of LT4, and bringing with them their diary, the box/bottle of the PPI that they are on therapy with and the used, partially used, and unused boxes of Tirosint®.

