## **10 ADVERSE EVENTS DESCRIPTION & REPORTING**

Adverse event definitions and classification are reported in [Appendix I](#).

All the occurred adverse events (AEs), independently from their classification, must be reported on the CRF in the “adverse event” section.

A dedicated form is required for the reporting of the Serious Adverse Events (SAE form).

All the Serious Adverse Events (SAE) which occur during the clinical trial, independently of their causal relationship, must be reported immediately (i.e. within 24 hours after first knowledge) by fax or email to:

The collection period of AEs/SAEs for each subject starts from the signature of the informed consent until the end of the study and/or the follow-up planned period.

When the Investigator has received knowledge of an SAE, he/she should fulfill a SAE form (Type of report: initial) with the support of the **Study Coordinator/Monitor**, if necessary, and send it to  by fax or email as soon as possible but within 24 hours.

The preliminary notification should include, at least, this minimum information:

- 1) EUDRACT (if applicable) and protocol numbers;
- 2) Patient’s identification (initials - only when applicable according to local regulations- screening/randomization number, date of birth, gender), relevant medical history;
- 3) SAE description and its onset;
- 4) Investigator’s causality assessment on the event relationship with the study medication;
- 5) IMP batch N°, first admin- and last admin before SAE, if code broken – when applicable;
- 6) Specific treatment of the SAE;
- 7) Investigator: name, address, phone number.

SAEs must be monitored until resolution or acceptable stabilization in the event of chronicity.

In case of death, the Investigator will be requested for forwarding the autopsy report, if available.

When the investigator receives additional information regarding the initial SAE, he/she should fill in a new SAE form and tick the “Follow Up” box and fax or email it within 48 hours to the .

All SAEs, qualified for the reporting to FDA, will be submitted to FDA by IBSA or its delegate according to the post-marketing pharmacovigilance reporting requirements, within **15 calendar days** from IBSA's first knowledge.

Follow-up reports will be reported within 15 calendar days of receipt of new information or as requested by FDA.

The clock for expedited reporting (day 0) starts as soon as the information containing the minimum reporting criteria has been received by IBSA.

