## **19 APPENDICES**

## **Appendix I**

### ***ADVERSE EVENTS***

#### ***DEFINITIONS AND CLASSIFICATION***

##### ***1. Adverse events (AEs) and their classification***

*Any untoward medical occurrence in a patient or clinical investigation subject administered a medicinal product and which does not necessarily have to have a causal relationship with this treatment.*

An adverse event can therefore be any unfavourable and unintended sign (including an abnormal laboratory finding, for example), symptom, or disease temporally associated with the use of a medicinal product, whether or not considered related to the medicinal product.

All adverse events will be classified according to the categories **Serious/Non-Serious, Expected/Unexpected** and **Mild, Moderate** and **Severe**. In addition, the physician responsible for the patient will always be asked to indicate whether a causal relationship exists between the specified event and the study drug.

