#### *MILD*

Symptom barely noticeable to study subject and that does not influence performance or functioning. Prescription drug not ordinarily needed for relief of symptom but may be given because of subject’s personality.

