*M. to administer drug only in accordance with the approved protocol and to participants under the investigator's personal supervision or under the supervision of a co-investigator; to not supply the investigational drug to any person not authorized;*

*N. to explain the correct use of the investigational products to each subject and check that each subject is following the instructions properly.*

*O. to maintain adequate records of the disposition of the drug, including dates, quantity, batch number, expiry date, code number and trial subject number and use by each participant. If the investigation is terminated, suspended, discontinued, or completed, the investigator shall return the unused supplies of the drug to the sponsor, or otherwise provide for the disposition of the unused supplies of the drug (only under Sponsor's request).*

*P. to reconcile all investigational products received by IBSA.*

*Q. to store the investigational products as specified by IBSA.*

*R. to adhere to the protocol and make no amendment to the study protocol without prior discussion and written agreement with the Study Monitor and the Sponsor, except where necessary to eliminate an immediate hazard to trial subjects, or when the changes involve only logistical or administrative aspects of the trial (e.g. change in monitor, change of telephone numbers, etc.);*

*S. to document and explain any deviation from the approved protocol.*

*T. to collect, record and report data properly on the CRFs according to the instructions therein and to ensure that only authorized staff signs the pages of these documents;*

*U. to evaluate and to record all AEs and/or laboratory abnormalities occurring within the clinical study and evaluate their seriousness based on the protocol and provide medical care as indicated and documented appropriately; to notify the Study Monitor and the contact person of the Sponsor regarding adverse events as appropriate according to the rules laid down in the appendix pertaining to adverse events and the attached to this protocol;*

- V. to report immediately all Serious Adverse Events (SAEs) to IBSA, except those SAEs that protocol or other documents as IB identifies as not needing immediate reporting.*
- W. to ensure adequate medical care to subjects for any adverse events, including clinically significant laboratory values, or intercurrent illnesses occurring during the trial;*

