### 9.5.2 Adverse Events

Adverse events (AEs) intensity and frequency will be analysed during the pre-treatment phase and in the treatment phase until End of Study Visit.

The following summary tables will be provided:

- Adverse Events by SOC and PT;
- Serious Adverse Events by SOC and PT;

- Drug related Adverse Events by SOC and PT;
- Pre-Treatment Adverse Events by SOC and PT;
- Serious Pre-Treatment Adverse Events by SOC and PT;
- Treatment-Emergent Adverse Events by SOC and PT;
- Serious Treatment-Emergent Adverse Events by SOC and PT;
- Drug related Treatment-Emergent Adverse Events by SOC and PT;

Serious adverse events and fatal adverse events will also be listed.

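### The visit instructions make thyroid symptoms adverse events on condition of an undefined clinical significance, which conflicts with the protocol's rule to record every adverse event, so these symptoms may be under-recorded

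*Protocol*

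**What the plan says.** Protocol 7.3 (Visits 2 and 3) and 7.4 (Visit 4) carry one identical sentence on new or worsened signs and symptoms of hypo- or hyperthyroidism. Those "reported by the patient, if clinically significant, will have to be recorded as adverse events". Palpitations are the example given. Protocol 7.2 (Visit 1) puts a parallel condition on history: such symptoms "reported by the patient at the screening visit, if clinically significant, will have to be recorded as medical history in the CRF". Neither document defines clinical significance.

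The general rules contain no such condition:

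- Section 10: "All the occurred adverse events (AEs), independently from their classification, must be reported on the CRF".
- Appendix I, definition: "An adverse event can therefore be any unfavourable and unintended sign (including an abnormal laboratory finding, for example), symptom, or disease".
- Appendix I, mild grade: "Symptom barely noticeable to study subject and that does not influence performance or functioning".
- Appendix III, item U, makes it the investigator's duty "to evaluate and to record all AEs and/or laboratory abnormalities occurring within the clinical study".

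SAP 9.5.2 builds its safety tables on what is recorded: "Adverse events (AEs) intensity and frequency will be analysed during the pre-treatment phase and in the treatment phase until End of Study Visit". It lists tables by system organ class and preferred term for pre-treatment, treatment-emergent, serious and drug-related events.

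**The concern.** The trial switches patients from tablets to capsules at the same dose, on the hypothesis that capsule absorption is less affected by proton pump inhibitors. If absorption changes, symptoms of too much or too little thyroid hormone are the natural clinical consequence. These are the symptoms to which the visit text attaches a significance test.

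Several of the hypothyroid features listed in protocol 2.1, such as tiredness, dry skin and poor memory, are non-specific and easily set aside as not significant. The person judging knows the treatment and works under a protocol that expects no LT4-related adverse events (section 4, on patient safety). There is no concurrent arm to which the same filter applies, so the absolute count is the safety result. A low thyroid-symptom rate could be read as good tolerability of the switch when it partly reflects the recording instruction.

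**Working it through.** The plan states no figure on this point, so the check is mainly a comparison of texts.

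**1. A test case.** A patient reports at Visit 3 a new palpitation that is barely noticed and does not affect functioning. The investigator judges it not clinically significant.

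- Appendix I definition: an unfavourable, unintended symptom, hence an adverse event.
- Appendix I severity: it fits the mild grade.
- Section 10: it goes on the CRF.
- Appendix III, item U: the investigator must record it.
- Section 7.3, Visit 3: the instruction does not call for it, because the condition fails.

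Four texts require the record and one does not. No text says which prevails.

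**2. Where each instance acts.** At Visit 2, adverse events are reviewed before the first capsule, so that instance bears on pre-treatment events. Visits 3 and 4 bear on treatment-emergent and drug-related events.

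**3. Other routes for the symptoms.** Protocol 9.3 and SAP 7.2 list adverse events, physical examination, vital signs and weight (SAP 7.2 adds compliance). There is no symptom scale, and the diary covers drug intake. Patient-reported thyroid symptoms therefore reach the SAP 9.5.2 tables through the adverse event form alone.

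**4. Direction.** Two effects oppose each other. The filter at Visits 3 and 4 can remove events. The filter at Visit 1 can leave a tablet-period symptom out of medical history; if it is recorded after the switch, it looks new and adds an event. Write

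recorded patients = N × (r × s + m)

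where N is the number treated, r the true share with a new or worsened thyroid symptom, s the share of those judged clinically significant, and m the share with an old symptom counted as new. The count is too low when m < r × (1 − s) and too high when m is larger. The documents give none of r, s and m.

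**5. Scale, by assumption only.** N = 47 (SAP 4.1). Assume r = 10% to 30%, s = 25% to 75%, every site using the visit sentence as an exclusion, and m = 0:

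| r | True patients, 47 × r | Recorded at s = 25% | Recorded at s = 75% |
|---|---|---|---|
| 10% | 4.7 | 1.2 | 3.5 |
| 20% | 9.4 | 2.4 | 7.1 |
| 30% | 14.1 | 3.5 | 10.6 |

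At r = 20% and s = 50%, 9.4 × 0.5 = 4.7 patients are lost. Five old symptoms counted as new would then reverse the sign. The table shows how the effect would scale and is not an estimate.

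**The case against.** The strongest reply is that the visit sentence creates a duty and forbids nothing. It says what must be recorded and does not say that other symptoms are left out. Each of the Visit 2, 3 and 4 lists has an unconditional adverse event item, protocol 9.3 says events are recorded at every visit, and section 10 binds throughout. The adverse event form page shown in Appendix I grades severity and has no significance field. A site reading the whole protocol would record the mild palpitation. This stands to the extent that under-counting is possible and not established. It does not remove the conflict: a condition attached to one class of symptom is naturally read as a filter, and sites could reasonably differ.

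A second reply is that the main safety check on the switch is biochemical. TSH, FT4, FT3 and TT3 are measured at Visits 3 and 4 and summarised as low, normal or high (SAP 9.5.1). Heart rate, blood pressure and weight are also taken at the final visit. None of this depends on the sentence. That stands, and it limits the consequence.

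A third reply is that Appendix III, item W, uses similar language about clinically significant laboratory values. That item concerns medical care and not what is recorded, so it shows no comparable filter elsewhere.

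A fourth reply is that the study has ended, so protocol wording can no longer change the data. That is true, and it is why the fix has a separate part for data already collected.

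**Conclusion.** The conflict is real and should be resolved. Where sites followed the visit text, thyroid symptoms judged not clinically significant may be missing from the tables: pre-treatment events through Visit 2, treatment-emergent events through Visits 3 and 4. Tablet-period symptoms may be missing from medical history through Visit 1. The primary TSH analysis and the sample size are untouched.

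Neither the size nor the net direction can be derived from the documents. They give no symptom rate, no share judged significant, and no account of which instruction sites applied.

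A reader might infer three stronger things that the documents do not support:

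- That thyroid symptoms are certainly under-counted. Section 10 still bound the sites, and the Visit 1 condition can push the count upward.
- That mild thyroid events are largely removed. Severity is graded by noticeability and effect on functioning, and nothing equates mild with not clinically significant.
- That the reported rates are lower bounds. That would require knowing that sites used the visit sentence as an exclusion and that no old symptom was counted as new.

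**What to change.** Reconcile the passages. Delete the words *if clinically significant* from the adverse event sentence at Visits 2, 3 and 4, and from the medical history sentence at Visit 1. All such symptoms are then recorded, and those that are new or worsened are graded under Appendix I. The cost is wording in four places, a few more mild adverse event records and a slightly less favourable adverse event rate.

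For the data already collected (47 treated, 45 completed), add a statement to SAP 9.5.2 and to the report. It should say that the protocol's two recording instructions differed, describe which one sites followed, and note that thyroid-symptom rates may be under-recorded where the visit instruction was applied. It should not call the rates lower bounds. The cost is a query to the sites and a short paragraph.
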